1.2 DRUG PROFILE

[figure not shown]
1.2.1 BI 754111

BI 754111 is a humanised IgG4Pro mAb against LAG-3 that is being developed as an intravenous (i.v.) infusion for the treatment of cancer. BI 754111 has highly human frameworks and a low predicted immunogenicity score. The BI 754111 molecule has a molecular weight of approximately 149 kilodaltons. The antibody is composed of 2 heavy chains (448 amino acids each) and 2 light chains (214 amino acids each). The 4 polypeptide chains of the antibody are linked together by disulfide bonds. Each heavy chain contains one consensus sequence for N-linked glycosylation.

1.2.2 [⁸⁹Zr]Zr-BI 754111

BI 754111 has been radiolabeled with Zr-89 using p-isothiocyanatobenzyl-desferrioxamine (Df-Bz-NCS) as a chelate. [⁸⁹Zr]Zr-BI 754111 was prepared according to a standard procedure ([R18-1541](#)). For a more detailed descriptions of [⁸⁹Zr]Zr-BI 754111 please refer to the current BI 754111 Investigator's Brochure (IB) and the related Investigational Medicinal Product Documentation (IMPD).

1.2.3 BI 754091

For a more detailed description of the BI 754091 and BI 754111 profiles please refer to the current respective Investigator's Brochures (IBs).

1.3 RATIONALE FOR PERFORMING THE TRIAL

Most patients with locally advanced or metastatic tumors will succumb to their disease, justifying the substantial need for novel therapeutic strategies to improve the outcome for patients with advanced or metastatic malignancies.

Proprietary confidential information © 2020 Boehringer Ingelheim International GmbH or one or more of its affiliated companies

Immune-checkpoint inhibition has been shown to be a promising therapeutic strategy in a subset of patients. The limited success achieved with checkpoint-inhibitor monotherapy (up to 80% of treated patients do not respond; [R15-3588](#), [R15-3778](#)) in some studies may, in Part, be attributed to redundancy in immune-checkpoint inhibitor pathways. Therefore, it is postulated that blockade of multiple checkpoint-inhibitor pathways may result in better anti-tumor activity and improved clinical outcome in a higher percentage of patients compared to checkpoint-inhibitor monotherapy. There is now sufficient evidence that blockage of the PD-1 pathway leads to over-expression of other checkpoint inhibitors, including LAG-3. This over expression of other checkpoint inhibitors may represent an escape pathway from the PD-1 pathway blockade. Therefore, it is possible that blocking multiple checkpoint inhibitors at the same time would lead to better response and potentially rescue some of the patients that have failed the PD-1 single-agent blockade, including patient with NSCLC ([R15-3696](#), [R16-0852](#), [R16-0868](#), [R16-0881](#), [R16-2707](#), [R16-5335](#), [R16-5545](#)). Multiple immune-checkpoint inhibitor combinations are currently in development including the combination of anti-PD-1 and anti-LAG-3 mAbs with encouraging preliminary results ([R16-5204](#), [R16-5218](#)).

New, more tolerable, combinations of immune-therapy treatment are needed to continue to improve the outcome for patients. BI 754111 in combination with BI 754091 has the potential to be such a combination.

Still, some aspects of LAG-3 expression and BI 754111 biodistribution (inside and outside the tumor lesions) remain unclear. For example, it is unclear which patients may benefit from combining anti-LAG-3 and anti-PD1/anti-PDL1 therapies. Even though tumor LAG-3 expression assessed on biopsies may serve as a predictive biomarker, this has limitations such as difficult to reach sites, low yields of tumor cells in the obtained bioptic sample, tumor heterogeneity resulting in sampling bias and risks for complications of the bioptic procedure (pneumothorax, bleeding). A non-invasive and more comprehensive way to study the expression of LAG-3 and the kinetic behavior of BI 754111 is needed. PET using radiolabeled BI 754111, i.e. [⁸⁹Zr]Zr-BI 754111, as tracer may offer a unique way of studying the interaction between LAG-3 expression and BI 754111 distribution. This non-invasive and repeatable technique may allow for studying the spatial and temporal variations in uptake of BI 754111.

Therefore, the aim of this study is to evaluate [⁸⁹Zr]Zr-BI 754111 PET imaging as a non-invasive method to determine the biodistribution of the therapeutic antibody at the site of action (i.e. in the tumor) and as a non-invasive method to determine LAG-3 expression at the site of action (i.e. in the tumor). These readouts are considered supportive to inform BI 754111 dose finding and potentially also for future patient selection.

Another aim of this study is to explore whether an association can be established between the tumor [⁸⁹Zr]Zr-BI 754111 uptake at baseline and the anti-tumor efficacy of BI 754111 therapy when combined with the anti-PD-1 BI 754091. It is assumed that [⁸⁹Zr]Zr-BI 754111 uptake will be related to LAG-3 expression. In addition, additional markers for the status of the immune system before/during therapy will be assessed in biopsies and blood samples to allow for better interpretation of the impact of LAG-3 overexpression as determined by LAG-3 immune PET in the context of other potential mechanisms of resistance. The combination of the major resistance mechanisms may vary in each patient.

Proprietary confidential information © 2020 Boehringer Ingelheim International GmbH or one or more of its affiliated companies

While LAG-3 is not expressed on peripheral T-cells in healthy volunteers or most patients with solid tumors, it appears to be expressed on T-cells of patients with HNSCC ([R18-1377](#)). In NSCLC tumors that responded to anti-PD-1/anti-PD-L1 therapy, increase in LAG-3 expression may be a mechanism of acquired resistance to anti-PD-1/PD-L1 therapy. Therefore, intratumoral expression of LAG-3 may be a good enrichment marker for patient selection for PD-1/LAG-3 combination therapy. Hence, in this study, we will include patients with HNSCC and NSCLC (upon progression after an initial response to anti-PD-1/anti-PD-L1 therapy) in order to measure LAG-3 receptor occupancy in this patient population.

The therapeutic benefit or specific adverse events in patients cannot always be anticipated during the trial setup. Later on there may be new scientific knowledge about biomarkers and other factors contributing to diseases or the action of a drug. In order to be able to address future scientific questions, patients will be asked to voluntarily donate biospecimens for banking (please see [Section 5.4](#)). If the patient agrees, banked samples may be used for future biomarker research and drug development projects, e.g. to identify patients that are more likely to benefit from a treatment or experience an adverse event (AE), or to gain a mechanistic or genetic understanding of drug effects and thereby better match patients with therapies.

1.4 BENEFIT - RISK ASSESSMENT

The role of the immune-checkpoint inhibitors within a normal immune response is to dampen the immune response after the trigger (antigen) is resolved minimizing collateral-immune-mediated damage to healthy tissue. Immune-checkpoint inhibitors also play a major role in promoting and maintaining self-tolerance by inactivating auto-reactive T-cells. Therefore, manipulation of immune-checkpoint-inhibitor pathways unleashes the immune system and comes with a higher risk of inducing immune dysfunction leading to immune-related adverse events (irAEs). Indeed, mice deficient in PD-1 or its ligands (PD-L1 and PD-L2) were found to be highly prone to development of autoimmune diseases ([R16-2362](#), [R16-2364](#), [R16-2968](#), [R16-2969](#), [R16-2970](#)).

[figure not shown]
Data from immune-checkpoint clinical trials show that irAEs occur frequently in patients treated with anti Cytotoxic T-lymphocyte-associated protein 4 (CTLA-4) (90%) and anti-PD-1 or anti-PD-L1 (70%) mAbs. However, the majority of these AEs are mild in severity ([R12-5176](#), [R15-3588](#), [R15-3715](#)) and occur within the first 4 months of initiating therapy ([R15-3780](#), [R16-0864](#), [R16-0899](#)). The irAEs affect mainly the gastrointestinal tract (including diarrhea and, less frequently colitis), skin (including rash/erythema and, less frequently vitiligo), endocrine glands (including hypothyroidism, hyperthyroidism, and hypophysitis), liver (frequently asymptomatic elevated transaminases), and lung (pneumonitis), but could also potentially affect other tissues. Rare fatal cases of colitis and pneumonitis have been reported with use of immune-checkpoint inhibitors. The main treatment of irAEs is the administration of steroids for 2 to 4 weeks; other immunosuppressive agents (such as infliximab, mycophenolate mofetil and cyclosporine) can be used in case of a steroid-refractory irAE ([R16-0763](#), [R16-0899](#)).

As previously mentioned, significant improvement in checkpoint inhibitor effect has been achieved with checkpoint inhibitor combination therapy. The combination of nivolumab and

Proprietary confidential information © 2020 Boehringer Ingelheim International GmbH or one or more of its affiliated companies

ipilimumab, for example, has resulted in significant improvement in ORR, compared to checkpoint inhibitor monotherapy in patients with NSCLC and melanoma ([R16-5545](#), [R15-3696](#), [R16-5544](#)). Unfortunately, the improved efficacy of combined nivolumab and ipilimumab was associated with a significant increase in the rate and severity of AEs. Grade 3 and 4 AE rates of 53% to 55% were reported with the full-dose combination of nivolumab and ipilimumab in patients with melanoma ([R15-3696](#), [R16-5544](#)) and 33% to 37% with reduced dose and dosing frequency of the ipilimumab component in NSCLC compared to approximately 10% for nivolumab monotherapy in these populations ([R15-3696](#), [R16-5544](#)).

Treatment with BI 754111 and BI 754091 is anticipated to be associated with a similar pattern of AEs. Immune-related AE management guidance will be provided in the trial documentation. Infusion-related reactions have been reported with checkpoint-inhibitor treatments. These reactions occur infrequently and are typically managed based on symptoms using treatments ranging from histamine antagonists in mild cases to administration of epinephrine when symptoms of anaphylaxis are detected. Detailed irAE management guidelines are presented in [Appendix 10.2](#).

Preliminary efficacy analyses indicate that there are 6 patients with Partial response (PR) and 20 patients with disease stabilization on BI 754091 monotherapy in the 1381-0001. The PRs were reported in 2 patients with triple negative breast cancer, 1 patient with fallopian tube cancer, 1 patient with renal cancer, 1 patient with stomach cancer *and one patient with endometrial cancer*. All of these PRs occurred in patients receiving the 240 mg q3w dose of BI 754091.

BI 754091 has also been administered in combination with BI 754111 (monoclonal IgG4pro antibody targeting the human LAG-3) to 86 patients with advanced/metastatic solid tumors in trial 1381.2. Fifty five of these patients have been treated with 240 mg BI 754091 in combination with increasing doses of BI 754111 (Q3W). In the dose expansion portion of the

Proprietary confidential information © 2020 Boehringer Ingelheim International GmbH or one or more of its affiliated companies

study, 31 patients have been treated with 240 mg BI 754091 in combination with 600 mg BI 754111 Q3W.

As of 30 November 2018, the combination treatment has been well tolerated with no DLTs occurring during the MTD evaluation period of the dose escalation part of the trial and no treatment related deaths have been reported. The most frequently reported AEs in patients treated with combination BI 754091 and BI 754111 were nausea (23.3%), fatigue (22.2%), diarrhoea (15.1%) and vomiting (15.1%). The majority of AEs were CTCAE Grades 1 and 2. Grade 3 and 4 AEs occurred at a frequency of 24.4% and 1.2 %, respectively. Of the grade 3 AEs, colitis, diarrhea (2 cases), infusion related reaction (2 cases), aseptic meningitis and maculopapular rash were reported as possibly related to study drugs. The only Grade 5 event was respiratory failure, occurring in the context of AEs pneumonia, sepsis and progressive disease. These events (including the fatal event) were unrelated to trial drugs.

Infusion related reactions have been reported in approximately 7% of patients treated with the combination of BI 754091 and BI 754111, none reported with BI 754091 monotherapy. The majority of the events were reported in patients receiving 240 mg of BI 754091 in combination with 600 mg of BI 754111, with 2 events reported in patients receiving 240 mg of BI 754091 in combination with 20 mg of BI 754111. The majority were of CTCAE Grade 2. Two events were Grade 3 events and led to treatment discontinuation. The reported infusion related reactions occurred during the infusion mostly at cycle 2 or cycle 3.

Preliminary efficacy data show 25 patients have achieved best response of stable disease (SD) to date and 3 patients have achieved best response of partial response (PR). PR was reported for 1 patient with anal cancer treated with 240 mg BI 754091 in combination with 200 mg BI 754111, 1 patient with microsatellite stable rectal cancer treated with 240 mg BI 754091 in combination with 600 mg BI 754111 and 1 patient with Triple Negative Breast Cancer (TNBC) treated with 240 mg BI 754091 in combination with 600 mg BI 754111.

Based on these pre-clinical and clinical data treatment with BI 754111 and BI 754091 is expected to provide patients with clinical benefit at an acceptable risk.

Risk linked to radiation burden: A single injection of 37 MBq 89Zr-mAb is expected to result in a radiation burden of ~ 20 mSv. In addition, every low dose CT scan adds 3 mSv to the radiation burden.

The first 3 patients in part 1 of the study will receive 2 injections of 89Zr-mAb followed by 5 PET scans (3 after the first and 2 after the second injection). This results in a radiation dose of 55 mSv.

The following patients in part 1 (maximum 2) will receive 2 injections of 89Zr-mAb followed by 4 PET scans. This results in a radiation dose of 52 mSv.

After administration, no shielding is required, and the subject can go home immediately. It is recommended that prolonged physical contact with small children (hugging, holding for more than a few hours per day) is avoided in the days following injection of 89Zr-mAb.

In part 2 five LAG-3 negative patients will receive 1 injection of 89Zr-mAb followed by 2 (before CTP 3.0) or 3 (after CTP 3.0) PET scans. This results in a radiation dose of 26 or 29 mSv.

Proprietary confidential information © 2020 Boehringer Ingelheim International GmbH or one or more of its affiliated companies

In part 2 up to 30 LAG-3 positive patients will receive 2 injections of 89Zr -mAb followed by 4 (before CTP 3.0) or 6 (after CTP 3.0) PET scans. This results in a radiation dose of 52 or 58 mSv.

All patients in this trial will undergo a diagnostic ^{18}F FDG-PET with a dose of 200 MBq, resulting in a radiation burden of 4 mSv, followed by a low dose CT of 3 mSv. Patients for whom FDG-PET is not part of standard of care, this will add 7 mSv to the total radiation dose related to the study.

Overall, the total radiation dose will represent 52 to 65 mSv.

Optimalisation of the radiation dose is achieved via splitting of the protocol in two parts. Optimal mAb dose for imaging will be established in part 1, whereafter the patients in part 2 will be imaged at this optimal dose.

In order to ensure the accuracy of quantitation, 37 MBq is the minimum level of activity that can be used per injection.

There are no risk increasing / decreasing factors.

Justification of this study is provided through the intended benefit of mitigating serious diseases in the future (category 3b).

In conclusion, the radiation burden for this study has been optimized, is justified and falls within the dose limits as discussed in NCS-26/ICRP-62 ([R18-2184](#))

Even so, patients should be advised of the potential risks of side effects from investigational trial treatments. While some may be anticipated, others may be rare and unknown with irreversible and/or life-threatening effects. Patients should also be advised that there are other unknown risks associated with Participation in a clinical trial.

Although rare, a potential for drug-induced liver injury (DILI) is under constant surveillance by sponsors and regulators. Therefore, this trial requires timely detection, evaluation, and follow-up of laboratory alterations in selected liver laboratory parameters to ensure patients' safety, see also [Section 5.2.6](#), adverse events of special interest (AESI).

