3.1 OVERALL TRIAL DESIGN AND PLAN

This is a Phase I open label, non-randomized bio-distribution trial to be conducted in one specialized center. The trial is divided in 2 Parts as described below in [Figure 3.1:1](#) and will be conducted in a staggered approach.

Part 1 – Dosimetry and feasibility assessment – up to 5 patients

Part 2 – Assessment of tumor uptake – up to 35 patients

[figure not shown]

Recommended exp. dose is the BI 754111 dose recommended for the expansion phase of trial 1381-0002.

Figure 3.1: 1 Overall design

- **Part 1** is intended to assess the dosimetry of $[^{89}\text{Zr}]\text{Zr-BI 754111}$, to optimize the imaging time window and the feasibility of $[^{89}\text{Zr}]\text{Zr-BI 754111}$ PET to assess tumor distribution and uptake of BI 754111. The BI 754111 dose administered in this Part will be the dose recommended for the expansion phase of trial 1381-0002. The whole body biodistribution of $[^{89}\text{Zr}]\text{Zr-BI 754111}$ will be assessed and optimal tumor uptake parameters will be developed. See [Figure 3.1: 2](#).

Proprietary confidential information © 2020 Boehringer Ingelheim International GmbH or one or more of its affiliated companies

[figure not shown]
PD= Progression of Disease Bx=Tumor Biopsy

Figure 3.1: 2 Part 1: dosimetry and feasibility assessment

- Part 2 will be initiated following a positive SMC decision after review of all available data from Part 1 in order to assess whether a blockade of $[^{89}\text{Zr}]\text{Zr}$ -BI 754111 has been demonstrated. Patients will be tested for tumor LAG-3 expression at screening. During cycle 1, all patients will undergo baseline PET assessments. During cycle 2 (on-treatment PET assessment), at least 2 doses levels of BI 754111 treatment will be explored in patients tested positive for tumor LAG-3 expression. At least 2 patients should be included per dose cohort. See [Figure 3.1: 3](#).

Up to five patients tested negative for LAG-3 expression will be included in Part 2. These patients will not be part of dose exploration but will be offered treatment with BI 754111 at the dose recommended for the expansion phase of trial 1381-0002. Hence, they will not undergo the on-treatment PET/CT assessment procedures.

After cycle 2, all patients will be treated at the recommended dose.

PD= Progression of Disease Bx=tumor biopsy PET/CT post $[^{89}\text{Zr}]\text{Zr}$ -BI 754111: 2 before CTP 3.0, 3 after CTP 3.0

Figure 3.1: 3 Part 2: assessment of tumor uptake

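### Does Section 1.4's overall radiation dose of 52 to 65 mSv misstate the exposure of the LAG-3-negative patients?

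*Protocol*

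**What the plan says.** Protocol Section 1.4 builds the radiation burden from three components. For the tracer, "A single injection of 37 MBq 89Zr-mAb is expected to result in a radiation burden of" about 20 mSv. For the scans, "every low dose CT scan adds 3 mSv to the radiation burden". For the screening FDG-PET/CT, in patients who would not have it as standard care, "this will add 7 mSv to the total radiation dose related to the study".

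The section then gives a total for each group:

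- **Part 1, first three patients:** two injections and five scans, 55 mSv.
- **Part 1, at most two further patients:** two injections and four scans, 52 mSv.
- **Part 2, LAG-3 negative:** "In part 2 five LAG-3 negative patients will receive 1 injection of 89Zr-mAb" with two or three scans, depending on protocol version. "This results in a radiation dose of 26 or 29 mSv".
- **Part 2, LAG-3 positive:** two injections with four or six scans. "This results in a radiation dose of 52 or 58 mSv".

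After the FDG-PET/CT paragraph comes the summary line: "Overall, the total radiation dose will represent 52 to 65 mSv". The section ends by concluding that the burden is optimised, justified and within the cited dose limits.

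Section 3.1 confirms the LAG-3-negative schedule: "Hence, they will not undergo the on-treatment PET/CT assessment procedures". Section 4.1.4 confirms that in Part 2 only LAG-3-positive patients have the second tracer injection.

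**The concern.** The summary line carries no restriction and follows a paragraph about all patients in the trial, so it reads as the range for everyone. Yet a whole planned cohort has a printed dose of half the stated lower limit (26 against 52 mSv). Adding the FDG-PET/CT does not bring the cohort into the range.

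This is the only overall total in the radiation-risk text, and it stands shortly before the statement that the burden is justified. A reader who took only that line would credit the LAG-3-negative patients with at least 52 mSv. If the line were also wrong at its upper end, or if the cohort figures had been miscalculated, the basis for the dose-limit conclusion would be in doubt. That is the possibility worth checking.

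**Working it through.** **Inputs (all from Protocol Section 1.4).** About 20 mSv per injection, 3 mSv per low-dose CT (one with each PET scan), and 7 mSv (4 + 3) for FDG-PET/CT when it is not standard care.

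**Formula.** Dose = 20 × injections + 3 × scans, plus 7 if FDG-PET/CT is counted.

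| Group | Injections | Scans | Calculation | Printed | With FDG-PET/CT |
|---|---|---|---|---|---|
| Part 1, first three | 2 | 5 | 40 + 15 = 55 | 55 | 62 |
| Part 1, next two | 2 | 4 | 40 + 12 = 52 | 52 | 59 |
| Part 2 negative, before version 3.0 | 1 | 2 | 20 + 6 = 26 | 26 | 33 |
| Part 2 negative, after version 3.0 | 1 | 3 | 20 + 9 = 29 | 29 | 36 |
| Part 2 positive, before version 3.0 | 2 | 4 | 40 + 12 = 52 | 52 | 59 |
| Part 2 positive, after version 3.0 | 2 | 6 | 40 + 18 = 58 | 58 | 65 |

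All six printed cohort doses reproduce.

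**The summary line.** Among two-injection patients the minimum is 52 mSv (four scans, no FDG-PET/CT) and the maximum is 58 + 7 = 65 mSv (six scans, with FDG-PET/CT). That is the stated range exactly. Over all groups the range is 26 to 65 mSv, where the lower end excludes FDG-PET/CT and the upper end includes it. On a single basis it is 26 to 58 mSv without FDG-PET/CT and 33 to 65 mSv with it.

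**Size of the gap.** FDG-PET/CT has to be treated the same way on both sides.

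- Without it, the two-injection minimum is 52, so the gaps are 52 − 26 = 26 and 52 − 29 = 23 mSv.
- With it, the two-injection minimum is 59, so the gaps are 59 − 33 = 26 and 59 − 36 = 23 mSv.

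Setting 33 or 36 against 52 would mix the two bases and make the gap look smaller than it is.

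**Share of patients.** At most 5 of 40, or 12.5%. Both numbers are planned ceilings, because Sections 3.1 and 3.2 give five as a maximum for this cohort and 40 is the maximum enrolment.

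**Does anything use the lower limit?** Nothing in the SAP text takes a dose in mSv as input. The primary analysis in SAP Section 7.4.1 works on SUVpeak, and SAP Section 7.7 summarises exposure as the number of treatment cycles initiated. The dose-limit conclusion in Protocol Section 1.4 bears on the highest exposure, and 65 mSv reproduces.

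**The case for a change.** The best case for acting is that the line is current text, not a leftover. Its upper limit of 65 mSv needs the six-scan schedule of version 3.0, so the line was brought up to date and still omits a cohort listed just above. Amendment 1 revised this section in order to describe the radiation risk better, and a few added words would settle the matter. All of that is true, and the inconsistency is real. It does not show that anything would come out differently. The correct cohort figures stand in the same section, so anyone who needs the dose for a LAG-3-negative patient has it, and the summary errs towards more exposure.

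A second argument concerns the Part 1 scan count. Section 1.4 gives the fifth scan to the first three patients only. Section 3.2, flow chart footnote 7 and the note to blood-sampling Table 1 tie the dosimetry scan to Part 1 without that limit. For the fourth and fifth Part 1 patients this is 52 against 40 + 15 = 55 mSv (59 against 62 with FDG-PET/CT). The passages do differ and must be reconciled if that text is reissued, but the difference is 3 mSv for at most two patients and stays inside the stated range.

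The argument goes further only if footnotes 7 and 8, which add a third scan per cycle without naming a Part, are applied to Part 1 on top of the dosimetry scan. Other places in the protocol speak against reading them together. Section 1.4 applies the third scan to Part 2 only, and the note in Section 3.1 sits under the Part 2 figure. Table 3, the Cycle 1 schedule after the amendment, lists no dosimetry scan. SAP Section 7.4.1 adds that no patient was imaged under version 3. A higher upper limit on that basis would be conjecture.

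**Conclusion.** The observation is correct but leads nowhere. The 52 to 65 mSv line describes two-injection patients and does not say so. For the up to five LAG-3-negative patients, the section's own totals are 26 or 29 mSv (33 or 36 mSv with FDG-PET/CT), a gap of 26 or 23 mSv on a consistent FDG-PET basis.

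This is a missing label, not an error of calculation. Each cohort dose is right, and so is the upper limit. The slip overstates exposure for at most 12.5% of planned patients, and supplying the label would alter no procedure, dataset, estimate or conclusion. The practical value is smaller still because the trial was stopped early (SAP Section 4).

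The conclusion rests on Section 1.4's own unit doses, of which the tracer value is approximate, and on its own scan counts. It would need another look only if reconciling the Part 1 scan counts raised a total above 65 mSv. The one unconditional difference there is 3 mSv and does not.
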